2. STUDY DESIGN:

2.1: Overview:

This study will be conducted as a single center, prospective, open-label evaluation of different methods of priming on the anti-influenza CD4 T cell and antibody response in young children. It is anticipated that this study will last 3 years, with approximately 1 year of follow up for each subject. The study objectives are to evaluate the specificity and functional potential of the CD4 T cell response and the quantity, breadth and avidity of the neutralizing antibody response following either influenza infection or receipt of different types of licensed influenza vaccine as follows:

- Primary objective: To comprehensively evaluate the specificity and functional potential of CD4 T cell responses on a single cell level using intracellular cytokine staining following restimulation with pools of HA and NP peptides

Secondary objectives will include:

- To assess the full spectrum of antigen-specific CD4 T cell cytokine and chemokine production using multiplex cytokine assays
- To perform in depth characterization of the specificity of the CD4 T cell response following influenza vaccination or infection by Elispot assay
- To evaluate the humoral immune response that develops in response to infection or administration of the LAIV or IIV vaccines
- To determine the frequency of HA-specific memory B cells established using these priming conditions
- To determine the influence of the CD4 T cell response on the breadth and avidity of the post-vaccination antibody response using arrayed imaging reflectometry to rapidly quantify antibody levels against multiple HA proteins, microneutralization assays to quantify neutralizing antibody titers against different viral strains, and enzyme linked immunosorbent assays to determine HA antibody avidity and quantify stalk reactive antibody

[figure not shown]

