- Between 6 and 12 months to participate in the vaccination arm of cohort 2 (cohort 2A)
- Between 3 and 12 months to participate in the natural infection arm of cohort 2 (cohort 2B)
- Gestational age of ≥ 37 weeks at birth
- Parent/guardian can provide informed consent
- Available for the duration of the study
- History of previous IIV administration **ONLY** for participation in cohort 1
- Acute illness documented to be due to influenza virus **ONLY** for participation in the natural infection arm of cohort 2 (cohort 2B)

b. Exclusion Criteria:

- Immunosuppression as a result of an underlying illness or condition (including HIV or a primary immunodeficiency syndrome)
- Active neoplastic disease
- Use of potentially immunosuppressive medications currently or within the past year (including chemotherapeutic agents) or chronic (>2 weeks) use of oral or inhaled steroid therapy
- A diagnosis of asthma requiring chronic controller medication
- Previous administration of influenza vaccine in the current influenza season
- Receipt of immunoglobulin or another blood product within the year prior to study enrollment
- An acute illness within the previous 3 days or temperature $>38^{\circ}$ on screening **EXCEPT** for participation in the natural infection arm of cohort 2 (cohort 2B)
- A contraindication to influenza vaccination **EXCEPT** infants between 3 and 5 months presenting with natural influenza infection whose only contraindication is their current age

3.3: Discussion of Subject Population:

The main objective of this Study is to evaluate the specificity and functional potential of the CD4 T cell response and the quantity, breadth and avidity of the neutralizing antibody response following influenza infection or vaccination. In order to eliminate potential confounding factors, we plan to exclude any subject who has an acute or chronic medical condition that may result in immunosuppression. Also excluded will be potential subjects that have recently received immunosuppressive medications or blood products that could potentially interfere with vaccine immunogenicity. This exclusion will include children with a history of asthma who require chronic controller medicines, including inhaled steroids. Children with only a history isolated wheezing not on chronic controller therapy will be allowed to participate, although they will not be administered LAIV.

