While some subjects will have their initial enrollment completed in the office of their primary care physician, this may not be possible on days when clinic space is limited. In this situation or when the family is recruited by letter, the subject will have their enrollment completed and study vaccine administered (when appropriate) in the University of Rochester VRU. Only staff experienced in the collection of samples from and the vaccination of children will perform study procedures.

Vaccine booster visit:

Infants undergoing vaccination in cohort 2A will have the option of either presenting to the VRU or their primary pediatric practice to receive their influenza vaccine booster dose. If parents opt to present to the VRU, the subjects will have an interval history and targeted PE completed, vital signs and weight obtained, and then will be administered a dose of IIV intramuscularly. If parents opt to obtain the booster dose of this vaccination in their primary pediatric clinic, follow up will be scheduled prior to exiting the clinic and this date recorded so that parents can be reminded of this appointment the day prior by phone.

Visit 2 (day 10/38 + 4 days/- 2 days):

Subjects will return to the VRU or have a home visit completed on day 10 following their presentation with influenza infection or their final influenza vaccination (this will be day 38 following the initial vaccination for infants requiring 2 doses of influenza vaccine). At this point, an interim history will be obtained with a targeted PE as appropriate. The memory aids will also be reviewed to document recent symptoms of illness or adverse events following vaccination. Following this, a nasal wash and a sample of peripheral venous blood will be obtained.

Visit 3 (day 24/52 +/- 4 days): Subjects will return to the VRU or have a home visit completed on day 24 following their presentation with influenza infection or their final influenza vaccination (this will be day 52 following the initial vaccination for infants requiring 2 doses of influenza vaccine). At this point, an interim history and targeted PE will be obtained and the memory aids will be reviewed. A nasal wash and a sample of peripheral venous blood will then be obtained.

Table 2: Study Schedule

	Study year 1			Illness visits	Study year 2		
	Visit 1 (d0)	Visit 2 (d10/38)	Visit 3 (d24/52)		Visit 4 (d0)	Visit 5 (d7)	Visit 6 (d21)
Medical history	X						
Vital signs	X	X	X	X	X	X	X
Complete PE	X				X		

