Microneutralization assays: MDCK cells will be grown to confluence in a 96 well plate. Serial dilutions of serum will be preincubated with virus and transferred to MDCK cells to allow unneutralized virus to infect the cells. Free virus is then washed away and the plate is incubated to allow cytopathic effect to occur. The antibody titer is the highest serum dilution able to prevent MDCK cell infection.

ELISA: Plates will be coated with HA or NP protein and then incubated with dilutions of serum. After washing and blocking nonspecific binding, plates are incubated with a horseradish peroxidase-conjugated goat anti-human IgG antibody and developed with 3,3',5,5'-tetramethylbenzidine dihydrochloride substrate with absorbance read at 450 nm. To determine antibody avidity, sera are incubated on a recombinant HA-coated plate in the presence of serial dilutions of sodium thiocyanate. The serum avidity is defined as the concentration of sodium thiocyanate that induces 50% inhibition of antibody binding.

5.4: Safety Assessments:

As IIV and LAIV are well characterized childhood vaccinations currently recommended by ACIP (18) and the AAP (17), we do not expect any serious adverse events to occur. However, we will provide the parents with a post-vaccination memory aid and instruct them to record any adverse events that develop over the course of the study. An interval history will be obtained, including the development of any adverse events, and the memory aid will be reviewed at each subsequent study visit. Solicited systemic AEs will include feverishness, fussiness, vomiting, and headache. Solicited local AEs will include URI symptoms or injection site pain, redness, or swelling. The investigator will be responsible for monitoring and recording all AEs that are observed or reported during the study, regardless of their relationship to study product.

5.5: Assessment of Subject Compliance:

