$$y_{kit} = \alpha_k + \beta_k G(i) + \gamma_{kt} + \delta_{kit}. \quad (0.1)$$

Here y_{kit} represents the k th response variable measured from the i th subject at the t th time point; α_k is the overall mean value of y_{kit} ; $G(i)$ is a binary variable which equals 0 if the i th subject is vaccinated with LAIV and 1 otherwise; β_k is a linear coefficient that quantifies the magnitude of the group-effect; γ_{kt} is a random effect term that quantifies the time effects; and δ_{kit} represents independent measurement errors. Likelihood ratio test will be used to test $H_0: \beta_k = 0$ against $H_1: \beta_k \neq 0$. **Aim 2:** Two groups of infants will be recruited for this aim. The first group (n=30) will receive a prime-boost IIV series; the other group (n=15) consists of infants who are infected by influenza naturally. Multiple clinical endpoints will be recorded at 3 time points for both groups. We will apply two sample *t*-test (or Wilcoxon rank-sum test, if Shapiro-Wilks test rejects the assumption of normality) at each time point to detect significant group differences. In addition, we will apply a linear mixed effect model similar to Equation (1.1) to detect the overall group effect. The resulting *p*-values will be properly adjusted to control for FDR at a 0.05 level. **Aim 3:** All subjects (four subgroups; n=105) will be followed longitudinally for a year and then be revaccinated with IIV. CD4 T cell responses, antibody responses, and transcriptional profile (high-throughput RNA-seq) will be measured at three time points: prior to IIV re-vaccination, d10 and 24 days post re-vaccination. We will apply one-way ANOVA *F*-test (or Kruskal-Wallis test, if the normality assumption is rejected) to detect significant group differences at each time point. Post-hoc analysis based on Tukey's adjustment will be used to test for significant differences between groups. We will also apply a linear mixed effect model similar to Equation (1.1) to detect the overall group effect. For high-throughput transcriptional data, first we will apply suitable pre-processing techniques such as non-specific filtering (81), normalization (82) and batch-effect removing

(83). We then select differentially expressed genes at each time point by specialized procedures such as DEseq (84) and DEGseq (85). Benjamini-Hochberg procedure will be used to control FDR at a 0.05 level for all analyses.

13.3: Data and Safety Monitoring:

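### Aim 2 compares measured infant antibody levels without a baseline or age term, so residual maternal antibody would be counted as response in the secondary antibody contrasts

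*Combined protocol and SAP*

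**What the plan says.** Section 13.2 compares 30 vaccinated infants (2A) with 15 naturally infected infants (2B) at three visits, using a two-sample t-test or rank-sum test "at each time point to detect significant group differences". A mixed model like the one for Aim 1 estimates an overall group effect. It contains group and time, and no age or visit 1 covariate.

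Four other places matter:

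- **Ages and gestation (section 3.2).** 2A takes infants of 6-12 months and 2B infants of 3-12 months. All are born at term.
- **Assays (section 5.3).** In the ELISA, "plates are incubated with a horseradish peroxidase-conjugated goat anti-human IgG antibody", so the signal is human IgG of whatever origin. Microneutralisation reports a titre. No rise from baseline is defined for either.
- **Timing (section 5.1).** Visit 3 is day 24 after presentation in 2B. In 2A, "this will be day 52 following the initial vaccination for infants requiring 2 doses of influenza vaccine". Visit 2 is correspondingly day 10 against day 38.
- **Passive antibody (section 3.2).** The only rule excludes "Receipt of immunoglobulin or another blood product within the year prior to study enrollment". Maternal antibody is not mentioned anywhere.

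The relevant secondary objective (section 2.1) is "To evaluate the humoral immune response that develops in response to infection or administration of the LAIV or IIV vaccines".

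**The concern.** A term infant carries its mother's IgG, which wanes with age. Any that remains adds to the antibody the infant makes itself, and these assays cannot tell the two apart. The objective concerns antibody that develops after exposure. A raw level at visit 2 or 3 measures that antibody plus whatever remains of the mother's.

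Two design features push the maternal part the same way. The infection arm has the lower age floor, and in the vaccine arm the maternal part has about 28 more days to decay between the enrolment draw and each later draw. Both favour a higher level in 2B for a reason unrelated to priming. A secondary finding that infection induces more antibody than inactivated vaccine could then be partly the mothers' antibody. The mixed model has the same weakness: its group effect pools all three visits, including visit 1, where any maternal difference is least diluted.

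**Working it through.** **The plan's own figure.** Section 13.1 gives power 0.871 for Aim 2 (30 v 15, difference 0.4, SD 0.4, log10 scale). The noncentrality is (0.4/0.4) x sqrt(30 x 15/45) = 3.16 with 43 degrees of freedom. At two-sided 0.05 this returns 0.871, so the figure reproduces. It refers to CD4 T cells, and passive IgG does not enter that measurement.

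**Timing, from sections 2.2 and 5.1.** The dose interval is 28 to 42 days and the visit windows are +4/-2 and +/-4 days.

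| | 2A, days from enrolment draw | 2B |
|---|---|---|
| Visit 2 | 28+10-2 = 36 to 42+10+4 = 56 | 8 to 14 |
| Visit 3 | 28+24-4 = 48 to 42+24+4 = 70 | 20 to 28 |

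The ranges do not overlap.

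**Maternal component alone.** Half-life h is assumed. The log10 difference is 0.301 x (difference in days)/h.

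- Infants of equal age, 28 extra days in 2A: 0.301 x 28/25 = 0.34, or 0.301 x 28/40 = 0.21.
- Even ages (means 7.5 v 9 months, a gap of 1.5 x 30.44 = 45.7 days), at visit 3: 0.301 x 73.7/25 = 0.89, or 0.301 x 73.7/40 = 0.55.

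**Effect on the measured titre.** The assay reads log10(R + M), with R the infant's own antibody and M the maternal remainder, so the shift is smaller. Take R = 1, M = 2 at 3 months and h = 40:

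- 2B infant enrolled at 3 months, visit 3: M = 2 x 2^(-24/40) = 1.32, and log10(2.32) = 0.365.
- 2B infant enrolled at 7.5 months: M = 2 x 2^(-161/40) = 0.123, and log10(1.123) = 0.050.
- 2A infant enrolled at 9 months: M = 2 x 2^(-234.6/40) = 0.034, and log10(1.034) = 0.015.

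The youngest infected infants therefore carry almost all of the bias.

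**Simulation.** 30 v 15 infants, equal true response, SD 0.4 (the CD4 planning value, borrowed as a yardstick), h = 25 or 40 days, maternal titre at 3 months 0.5 to 2 times R.

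| Visit 3 analysis | Bias, 2B minus 2A (log10) | False-positive rate |
|---|---|---|
| Raw level, even ages | 0.02 to 0.09 | 0.04 to 0.12 |
| Raw level, 2B aged 3-6 months | 0.06 to 0.24 | 0.07 to 0.51 |
| Visit 1 titre and age as covariates, both age patterns | 0.00 to 0.12 | 0.04 to 0.08 |
| Simple change from visit 1, even ages | -0.15 to -0.26 | 0.19 to 0.38 |

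Repeat runs put the upper end of the second row between 0.51 and 0.57. With both arms aged 6-12 months, the raw bias is at most 0.02.

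The visit 1 contrast, which the plan also tests, shows 0.17 to 0.32 log10 with even ages and is significant in 0.50 to 0.76 of runs. That difference in titre is real, but in the simulation it is entirely maternal.

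**Precision.** The unadjusted standard error is 0.4 x sqrt(1/30 + 1/15) = 0.126. With visit 1 titre and age it is 0.12 to 0.14 for even ages, and about 0.20 to 0.23 if the arms barely overlap in age. Adding days since visit 1 raises it to 0.51 to 0.57.

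**The case against.** The strongest reply is that the stakes are low and the size rests on assumptions. The primary endpoint is CD4 T cells, the hypothesis about infants in section 1.1 concerns CD4 T cells only, and half-life, starting titre and age distribution are all absent from the documents. With evenly spread ages the visit 3 bias is small. All of this stands.

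Several stronger readings are tempting, and the documents do not support them:

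- **That maternal antibody is in fact higher in the infection arm.** Only the age floors differ. Both arms run to 12 months, and no enrolled ages or maternal titres are given. It is an expectation.
- **That the measured titre is shifted by 0.55 to 0.89 log10.** Those figures describe the maternal component alone. The infant's own antibody dilutes them in the total.
- **That visit 1 is ignored.** It is one of the three visits tested between arms, and section 2.2 says it assesses immunity at entry. An imbalance would be seen. It is simply not used as a covariate for the later visits.
- **That no maternal history is collected.** Section 10.1 says information on parents is gathered partly to deal with confounding, and the case report form is not among the documents. One can say only that no maternal influenza item and no covariate is named.
- **That the plan takes infant visit 1 IgG as proof of earlier exposure.** Eligibility rests on history, and section 5.5 judges missed infections by a rise between the last year 1 visit and year 2 day 0.

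The general statement in section 10.1 does not answer the point, because section 13.2 carries no adjustment through to the analysis.

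**Conclusion.** The point holds as a limited one. The planned Aim 2 antibody contrasts at visits 2 and 3, and the pooled group effect, contain no term that would separate residual maternal antibody from response, while age floor and sampling interval both favour a higher residue in the infection arm. The consequence runs from negligible to serious according to how many of the 15 infected infants are under about 6 months, which cannot be known from the documents. It is confined to secondary endpoints. Adjustment is worth making because the visit 1 sample is already drawn in both arms; it reduces the bias without removing it.

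**What to change.** In section 13.2, for Aim 2 antibody endpoints:

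1. Analyse log10 titre at visits 2 and 3 with arm, visit 1 log10 titre and age as terms. Take visit 1 out of the outcomes in the mixed model.
2. Add a sensitivity analysis limited to infants of 6-12 months in both arms.
3. State that a visit 1 antibody difference may be maternal.
4. Do not use simple change from visit 1. It subtracts the whole entry titre although only a fraction persists, and that fraction differs by arm because the decay intervals differ. The bias then reverses sign.
5. Do not add days since visit 1. It nearly duplicates arm and raises the standard error from about 0.12 to about 0.55.

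Optional: a visit 1 question on maternal influenza vaccination or illness in pregnancy, if the case report form does not already have one.

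Cost: analysis-plan wording, two degrees of freedom in 45 infants, and the loss of precision shown above. Some bias remains. Section 2.2 puts presentation typically at illness day 3-4, so a few 2B visit 1 samples may hold a little early infant antibody, which adjustment would partly remove from the response. The restricted analysis may be thin: with even ages about 15 x 6/9 = 10 infected infants remain, and hardly any if most are 3-6 months.

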1. PURPOSE OF THE STUDY AND BACKGROUND

1.1: Purpose of the Study:

Inactivated influenza vaccine (“IIV”) is an intramuscular vaccine administered to children ≥ 6 months in age that is composed of highly purified HA and NA surface glycoproteins and contains trace, if any, activators of the immune system. In contrast, live attenuated vaccine (“LAIV”) consists of intranasally delivered, attenuated viruses that stimulate the innate immune system while undergoing limited viral replication in the upper respiratory tract. Some children also continue to first encounter influenza through natural infection, where high levels of viral replication stimulate vigorous innate immunity. Although CD4 T cells play a key role in regulating the influenza-specific B cell, CD8 T cell, and innate immune responses, little is known about the immediate and long-term effects these different routes of early childhood priming have on CD4 T cell mediated immunity. The long-term goal of this research is to understand how a child’s early exposure to influenza shapes immunity and poises the immune system to respond to subsequent influenza challenge. Our objective is to determine how the anti-influenza CD4 T cell and antibody responses are altered by the mode of primary influenza encounter and establish the consequences this has on subsequent influenza vaccination. To accomplish this objective, we will enroll two cohorts of young children: 1) a cohort of 24 through 35 month of children administered either LAIV or IIV and 2) a separate cohort of infants first exposed to influenza through prime-boost administration of IIV or natural infection during their initial influenza season. All enrolled subjects will be followed longitudinally to the subsequent influenza season and then rechallenged with IIV. These cohorts of children will allow us to test the following hypotheses:

- 1) Compared to intramuscular IIV, initial exposure to intranasal LAIV establishes a greater and more polyfunctional CD4 T cell response in children 24 through 35 months of age
- 2) Compared to a first exposure to influenza through infection, primary infant vaccination with IIV establishes a more limited CD4 T cell repertoire that consists predominately of IL-2 producing cells, and
- 3) The CD4 T cell responses established with this initial priming will differentially poise subjects to respond to revaccination with IIV the following influenza season

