5. METHODS AND STUDY PROCEDURES

While our preference is for study visits to take place within the University of Rochester's Vaccine Research Unit, families will be given the option to complete visits 2, 3, 5, and 6, as well as any illness visits as home visits if this is more convenient for them. For a full description of the home visit protocol, please see the home visit addendum (section 5.11).

5.1: Study Schedule

Enrollment visit (visit 1, d0)

Subjects in the influenza vaccination groups will have a complete medical history obtained and demographic information collected, with particular attention to inclusion and exclusion criteria. If not already obtained, subject vital signs and weight will be measured. A directed physical exam will then be performed as indicated by medical history. Following this, a nasal wash and a sample of peripheral venous blood will be obtained. Subjects will then receive their initial influenza vaccination. Post vaccination, parents will be given memory aids to document adverse events following vaccination and the symptoms of any future illnesses that occur. They also will be instructed to call study personnel if symptoms consistent with an influenza-like illness develop.

Subjects recruited with potential natural influenza infection will have a complete medical history obtained with particular attention to current symptoms of illness and inclusion and exclusion criteria. If not already obtained, subject vital signs and weight will be measured. A directed physical exam will then be performed as indicated by the medical history. Following this, two nasal swabs will be obtained by placing UV-sterilized soft nylon flocked swabs into alternate nostrils of the infant and gently rotating them across the mucosa. One of these swabs will be used to perform a rapid influenza test, while the other will be placed into 1 mL of viral culture transport media for RT-PCR studies. Subjects with a negative rapid influenza test will not participate in the study further. Subjects that have a positive rapid antigen test will have the opportunity to consent to full study participation. If this consent is obtained, a nasal wash and a sample of

peripheral venous blood will be obtained. Parents will then be given a memory aid to document the progression of their current illness and the symptoms of any future illnesses that occur.

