13. DATA ANALYSIS AND MONITORING

13.1: Sample Size Determination:

	d=0.3	d=0.35	d=0.4
n1=25, n2=25	0.738	0.858	0.934
n1=30, n2=30	0.815	0.915	0.968
n1=35, n2=35	0.871	0.95	0.985
n1=30, n2=10	0.517	0.646	0.761
n1=30, n2=15	0.64	0.772	0.871
n1=30, n2=20	0.721	0.844	0.924

The primary endpoint of this study is CD4 T cell responses. Based on a study of immune response in children and adults (62), the overall mean percentage of IFN γ + CD4 T cells in 5-9 year old children vaccinated with IIV or LAIV is around 0.1%, or -3 in log₁₀ scale. The standard deviation (STD) in log₁₀ scale is around 0.4. The geometric mean differences induced by vaccinations or between the two types of vaccination is around 0.3 in log₁₀ scale. The above table summarizes statistical power based on Student's two sample *t*-test. Assuming our responses are similar, recruiting n=30 subjects in each group will give us adequate power (0.815) for Aim 1. Because LAIV is an attenuated virus, it is reasonable to assume that the difference in CD4 T cell responses induced by IIV and natural influenza infection is larger (d=0.4), therefore recruiting

n=30 subjects in the IIV group and n=15 subjects in the infection group can achieve adequate power (0.871) for Aim 2. For Aim 3, assuming that within-group STD is 0.4 and between-group STD is just 0.2, the power is 0.851 if we recruit n=105 subjects divided them into four subgroups (n1=30, n2=30, n3=30, n4=15).

13.2: Planned Statistical Analysis:

We outline the statistical analysis strategies for the specific aims as follows. **Aim 1:** A cohort of n=60 healthy children will be recruited and divided into two groups with equal sample size (n=30); one group will be vaccinated with LAIV and the other with IIV. Their T cell and antibody responses will be measured at three time points: Baseline, day 10, and day 24 post-vaccination. We will apply Shapiro-Wilk's test to check the normality. If the data passes the normality test, two sample *t*-tests will be used to detect significant mean difference between the two groups at each time point. Otherwise, Wilcoxon rank-sum test will be used. Because multiple response variables are used in this analysis, the *p*-values will be adjusted by the Benjamini-Hochberg multiple testing procedure (80) to control the false discovery rate (FDR) at the level of 0.05. In addition to pairwise comparisons, the following linear mixed effect model will be used to analyze data collected from all time points:

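### Aim 2 tests the infant arms at visit 1, a pre-vaccination sample in one arm and an acute-infection sample in the other, and on its natural reading averages that visit into the overall group effect

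*Combined protocol and SAP*

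**What the plan says.** Hypothesis 2 (section 1.1) concerns what each first exposure leaves behind: compared with infection, "primary infant vaccination with IIV establishes a more limited CD4 T cell repertoire".

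Section 5.1 describes visit 1 separately for the two routes of entry. In the vaccination groups, nasal wash and blood come first, and then: "Subjects will then receive their initial influenza vaccination". In the infection group, two nasal swabs come first. "Subjects that have a positive rapid antigen test will have the opportunity to consent to full study participation", and blood is drawn only once that consent is given. Section 2.2 puts illness presentation typically at day 3-4 after onset and describes cohort 2 as having no earlier influenza exposure. It also says that 2A responses are studied only after the second dose.

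For the Aim 2 analysis, section 13.2 says: "Multiple clinical endpoints will be recorded at 3 time points for both groups". A t-test or Wilcoxon test is applied "at each time point to detect significant group differences". It then adds: "In addition, we will apply a linear mixed effect model similar to Equation (1.1) to detect the overall group effect". The only equation printed is the Aim 1 model, introduced with the statement that a "linear mixed effect model will be used to analyze data collected from all time points". In it, the group term "is a linear coefficient that quantifies the magnitude of the group-effect", the time term is common to both arms, and the errors are independent. It has no group-by-time term, no baseline covariate and no term for the child.

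**The concern.** At visit 1 the 2A infants have met neither vaccine nor virus, while the 2B infants are already some days into an influenza illness. A difference at that visit cannot be read as imbalance before exposure, because 2B has been exposed. Nor can it be read as a difference in established responses, because 2A has none yet. No section gives visit 1 a separate role in Aim 2, calls its test descriptive, or leaves it out of the overall effect.

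Two readings of the results are at stake. A significant visit 1 test could be reported as a priming difference. And the single overall coefficient would mix one visit that does not address hypothesis 2 with two that do. It could then understate a real difference at days 10 and 24, or show one that is absent there.

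**Working it through.** **1. The three time points.** Aim 2 does not list them. Sections 2.1 and 2.2 give both infant arms the same year 1 draws: study entry, day 10 and day 24. In 2A the later two follow the second dose; in 2B they are counted from presentation.

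| | 2A (IIV) | 2B (infection) |
|---|---|---|
| Visit 1 | before first dose | after positive rapid test, about illness day 3-4 |
| Visit 2 | day 10 after final dose | day 10 after presentation |
| Visit 3 | day 24 after final dose | day 24 after presentation |

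**2. The plan's own figure.** Inputs from section 13.1: difference 0.4 log10, SD 0.4, n=30 and 15, two-sample t-test. Two-sided 5% is assumed because 13.1 does not state it. The standard error is 0.4 × √(1/30 + 1/15) = 0.1265 and the noncentrality is 0.4/0.1265 = 3.16 on 43 df. Power is 0.871, as stated. This describes a t-test at one visit, not the overall effect.

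**3. What one coefficient estimates.** With complete data and a time effect common to both arms, the group coefficient is the plain average of the visit differences:

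b = (D1 + D2 + D3)/3.

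Visit 1 therefore carries one-third weight. Take D2 = D3 = 0.40 (the plan's Aim 2 difference) and vary D1, which the documents do not give:

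- D1 = −0.2: b = 0.60/3 = 0.20
- D1 = 0: b = 0.80/3 = 0.27
- D1 = +0.2: b = 1.00/3 = 0.33
- D1 = +0.4: b = 1.20/3 = 0.40, no distortion

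On visits 2 and 3 alone, b = 0.40 in every case.

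**4. Precision and power when D1 = 0.** Let r be the within-child correlation (assumed; not in the documents) and let the analysis account for it.

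SE, three visits = 0.1265 × √((1+2r)/3); SE, visits 2-3 = 0.1265 × √((1+r)/2).

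| r | SE, three visits | SE, visits 2-3 | Power, three visits (b=0.267) | Power, visits 2-3 (b=0.400) |
|---|---|---|---|---|
| 0 | 0.073 | 0.089 | 0.946 | 0.992 |
| 0.3 | 0.092 | 0.102 | 0.806 | 0.969 |
| 0.5 | 0.103 | 0.110 | 0.714 | 0.946 |
| 0.7 | 0.113 | 0.117 | 0.635 | 0.918 |

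**5. The within-child term.** If errors are treated as independent, as in the printed equation, the variance of a child's mean over visits 2-3 is taken as 0.4²/2 when it is 0.4²(1+r)/2. The test statistic is then too large by √(1+r). At r = 0.5 this is 1.22, so the effective critical value is 1.96/1.22 = 1.60 and the true error rate is about 11%. It is about 9% at r = 0.3 and 13% at r = 0.7. Dropping visit 1 does not by itself give a 5% test.

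**6. False signal, for illustration only.** Suppose D1 is 0.2 to 0.4 and D2 = D3 = 0. The visit 1 t-test, before FDR adjustment, is significant with probability 0.34 at 0.2, 0.64 at 0.3 and 0.87 at 0.4; at 0.1 it would be about 0.12. The overall effect is 0.07 to 0.13. Its 5% test, with correlation modelled, rejects in 9-15% of trials at D1 = 0.2 and 21-43% at D1 = 0.4, for r from 0.7 down to 0.

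**The case against.** The strongest reply is that the damage is confined and its size unknown. The day 10 and day 24 tests are separate and untouched. The mixed model is supplementary and only similar to the Aim 1 equation, and Aim 2 never says outright that all three visits enter it. Section 2.2 already describes the enrollment draw as a measure of immunity at study entry and the day 10 draw as the one near the CD4 peak. All of this stands, and it limits the weight of the point. But nothing written uses that latitude: visit 1 is still tested, and the overall effect is given no other time frame.

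A reader might infer from step 6 that Aim 2 has a false-positive rate of up to 43%. The documents do not support that. They give no visit 1 difference, and a large early difference that vanishes by the expected peak runs against the plan's own account of timing. The match between two of the visit 1 probabilities and the section 13.1 table is arithmetic only, since that table concerns response differences. Its SD comes from vaccinated children aged 5-9.

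A reader might also attribute any visit 1 difference to illness alone. The primary assay uses influenza peptides with negative controls, so an early 2B difference may be part of the response to infection. It would then be real, but still not a comparison of established responses.

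The dilution comes from having one coefficient and no group-by-visit term, a form shared with Aim 1. What is particular to Aim 2 is that the same nominal visit is pre-exposure in one arm and post-exposure in the other.

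**Conclusion.** The point holds as a matter of what the overall effect estimates, and it should be corrected. Visit 1 cannot serve in Aim 2 as a baseline or as a response comparison, yet it is tested and, on the natural reading, given one-third weight in the overall effect. With no difference at visit 1, a 0.40 difference at days 10 and 24 becomes 0.27, and power at correlation 0.5 is 0.71 rather than 0.95. This rests on complete data, SD 0.4, two-sided 5%, modelled correlation and an assumed visit 1 difference of zero. Other values shift the estimate either way, and a visit 1 difference equal to the later ones leaves it unchanged.

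It would be wrong to conclude that the Aim 2 sample size or its day 10 and day 24 comparisons are compromised: the 0.871 reproduces and refers to a single-visit test. The harm is limited to the visit 1 test and the additional model.

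**What to change.** In section 13.2, Aim 2:

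- Report visit 1 descriptively, with 2B labelled acute-phase. Remove it from the between-arm tests and do not use it as a baseline covariate, since in 2B it is already post-exposure.
- Define the overall group effect as the average of the day 10 and day 24 group contrasts.
- Name one model in advance, with a within-child random effect or correlation: either visits 2-3 only, or all visits with group-by-visit terms. The two agree exactly only with complete data, and the protocol allows for failed blood draws, so the choice should be written down.

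The cost is wording, with no extra visits or blood. The standard error of the overall effect rises from 0.103 to 0.110 at correlation 0.5 (0.073 to 0.089 at 0; 0.113 to 0.117 at 0.7), and power for a 0.40 difference stays between 0.92 and 0.99. Days 10 and 24 remain imperfectly aligned, because 2A is timed from a second dose and 2B from presentation. A description of visits 2-3 by days since symptom onset or final dose would be useful but imprecise with 15 infected infants.
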